5.3 Selection of Investigational Device and Doses

Refer to [Section 3.2](#)

5.4 Treatments Administered

The pessary will be self-administered vaginally by the patient. The pessary should be inserted high into the vagina. The pessary should be used with the co-supplied vaginal tablet applicator. The patients should insert the applicator gently and deeply into the vagina, and then slowly depress the plunger to release the pessary. Instructions for use will be distributed to patients at the first site visit. See also [Section 5.1](#).

5.5 Method of Assigning Patients to Treatment Groups

Not applicable

5.6 Blinding

Not applicable

5.7 Prior and Concomitant Medication

Information about any concomitant medication, including OTC medications and vitamins taken by patients during the study and within 14 days prior to inclusion shall be documented in the eCRF. The generic name or trade name, dosage, and reason for use shall be recorded for all medications.

NOTE: Antibiotic medication during the study and within 14 days prior to inclusion is strictly prohibited

See [Appendix 1, Section 3](#) for specific questions.

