3.2.1 Risks and Benefits

The investigational device, Gedea Pessary has been evaluated in accordance with ISO 10993 (Biological Evaluation of Medical Devices). The evaluation included: cytotoxicity testing (Direct cell contact test, ISO 10993-5); *in vivo* irritation (Vaginal acute irritation; ISO 10993-10); and sensitization (local lymph node assay, ISO 10993-10). The *in vitro* cytotoxicity test, classified the test item as slight to moderate cytotoxic (scale 1–2 on a 3-grade scale); the *in vivo* irritation test as well as the *in vivo* sensitization test showed no signs of irritation, necrosis, or sensitization after treatment with Gedea Pessary.

The vaginal pessary may, in similarity with other vaginally administered products, cause temporary minor discomfort at insertion. The vaginal sampling procedures are similar to sampling procedures used in clinical practice and are unlikely to cause any major inconvenience to patients. In the Laccure pessary study,³⁸ there were no SAEs and vaginal itching was the most common AE.

There is a risk that patients will have no clinical benefit from the investigational device. This may cause patients to experience symptoms of BV including vaginal fishy smell, burning or irritation, pain during sexual intercourse, pain or discomfort when urinating, or abnormal vaginal discharge longer than necessary. However, an antibiotic will be offered on Day 14 if any symptoms should still be present, thus avoiding any risk associated with long-term untreated BV.

Subjects included in the study must refrain from using other intravaginal products to mitigate any risk of interactions with concomitant vaginally-administered products. The investigational

^a And on Day(s) 7, 9, 11, and 13 if receiving prolonged treatment

Protocol Version 2.1, 27 Jun 2019

LINK Medical Research | Protocol template

Version 2.0 | Effective date 17Apr2018

device acts locally on the vaginal mucosa and most likely will most likely not affect any concomitant systemic treatment.

Taken together, as the anticipated levels of discomfort are transient and mild, and that risks associated with long-term untreated BV are avoidable, the use of the investigational product appears to offer clinical benefits at a reasonable risk level.

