3.6 Early Withdrawal Procedures

See [Section 4.6](#) for withdrawal procedures. Patients refusing to visit the site for follow-up visits shall be contacted by telephone, if possible, to collect answers to the patient questionnaire, and AEs, if any. Patients receiving an antibiotic on Day 14 will be followed up for safety assessments.

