5.2.1 Rescue Medication

An antibiotic will be used as rescue medication in this investigation, and patients will receive a prescription according to clinical routines if considered necessary to relieve their BV symptoms on Day 14. Patients withdrawing at any point in the investigation may receive an antibiotic according to clinical routines if considered necessary by the Investigator. The dose of the prescribed antibiotic will be decided by the Investigator on an individual basis. The use of rescue medication will be recorded in the eCRF.

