Unless stated otherwise, the baseline value for a parameter is defined as the last non-missing value before the first self-administration of the study treatment by the patient. The first self-administration is to be performed on the same day as the first study visit (Day 0), after the study visit.

7.1.3 *Analysis relative day*

The analysis relative day for an assessment/value is defined as the time in days from the date of first administration of treatment to the date of the assessment. The date of first administration of treatment is considered as day 0.

7.1.4 *Analysis visit*

An analysis visit is defined as a categorical variable used to classify values within an analysis variable into temporal or conceptual groups used for analyses.

The visits as defined in the case report form, CRF, will be used as analysis visits.

In general, data from unscheduled visits will be presented in data listings only and not included in analysis or summary tables. An exception to this is data used to confirm eligibility in association with screening or randomisation where the last assessment will be considered in summaries of screening data.

7.1.5 *Handling of missing data*

The statistical analysis will be based on the observed data, i.e. no imputation is planned. In case of one or more missing symptom value(s) in the 3 BV symptoms, the sum of the 3 BV symptoms scores will be set to missing, see also [Section 8.7](#) below.

7.1.6 *Interim analyses*

Not applicable.

7.1.7 *Multiplicity*

Although there are two co-primary endpoints, no adjustment of e.g. p-values or confidence intervals will be applied. This is for two reasons, the first being that the evaluation of the second co-primary endpoint (safety and tolerability) will only be based on descriptive statistics and data listings, and the second is that both co-primary endpoints have to show favorable results.

For all other statistical analyses of the secondary endpoints, no adjustment due to multiple testing will be performed. It should be noted that the probability of making a type I error increases with the number of statistical tests performed.

7.1.8 *Subgroups*

Descriptive results of the primary clinical performance endpoint will be presented by study center, and by whether the patients at Day 0 reported 3 or more Bacterial Vaginosis infections during the last 12 months or not.

7.2 *Analysis sets*

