8.9 Proportion of patients receiving prolonged treatment

The proportion of patients receiving prolonged treatment is based on a binary variable which indicate whether a patient has received prolonged treatment or not, i.e. received study treatment on at least one of the days 7, 9, 11, or 13.

8.10 Proportion of patients receiving rescue treatment on Day 14

The proportion of patients receiving rescue treatment (an antibiotic treatment, as defined in the CIP) on Day 14 is based on a binary variable which indicate whether a patient has used rescue treatment or not, i.e. as shown by collected CRF concomitant medication data, where start date of the rescue medication should be from or after Day 14. Start and stop date of use of such rescue medication will be presented in data listings.

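### The protocol bans antibiotics for the whole study yet provides one on Day 14, states no in-study rule for BV that returns later, and the SAP can under-count those recurrences at Day 35/42

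*Protocol*

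**What the plan says.** **Antibiotic use**

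- Protocol 5.7, in a note: "Antibiotic medication during the study and within 14 days prior to inclusion is strictly prohibited". The note carries no exception and no cross-reference.
- Protocol 5.2.1 names two routes. One is a rescue prescription "if considered necessary to relieve their BV symptoms on Day 14". The other is withdrawal: "Patients withdrawing at any point in the investigation may receive an antibiotic according to clinical routines if considered necessary by the Investigator".
- Protocol 3.2.1 says that "an antibiotic will be offered on Day 14 if any symptoms should still be present, thus avoiding any risk associated with long-term untreated BV". The flow-chart text in 3.1 and the Day 14 visit in 3.5.10 place this antibiotic in the prolonged-treatment path.
- Protocol 3.5.9: for women cured on Day 7, Day 14 is a telephone contact, and no treatment step is listed.
- Protocol 3.6: "Patients receiving an antibiotic on Day 14 will be followed up for safety assessments".

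**Recurrence**

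- Protocol 2.2 makes recurrence a secondary endpoint on Days 14 and 35, or on Days 21 and 42 after prolonged treatment. The question in Appendix 1, Section 1 asks whether symptoms have come back to the point of needing medical care.
- SAP 8.8 takes a recurrence only from a *yes* at the visits where the question is scheduled. SAP 7.1.5 analyses observed data without imputation. SAP 7.1.1 sets a default denominator that includes patients with missing data. SAP 7.1.4 says that, in general, "data from unscheduled visits will be presented in data listings only and not included in analysis or summary tables".
- SAP 8.10 derives Day 14 rescue with the condition that "start date of the rescue medication should be from or after Day 14". SAP 7.9.2 lists that endpoint only for patients receiving prolonged treatment.

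**The concern.** There are two linked problems.

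The first is conduct. Read literally, 5.7 forbids what 3.1, 3.2.1 and 5.2.1 provide, because a woman given an antibiotic on Day 14 is still in the study. For BV that comes back after Day 14, the protocol states only the withdrawal route, yet it plans to ask women whether they need care for exactly that. Sites could reasonably act in different ways.

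The second is analysis. Whichever way a site acts, the SAP has no rule that turns an antibiotic or a withdrawal for returned BV into a recurrence. The women at risk of going uncounted are those who had the event, so any error lowers the recurrence rate and favours the product.

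**Working it through.** **Step 1. The antibiotic passages side by side**

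| Situation | 5.7 | 5.2.1, 3.1, 3.2.1 | SAP 8.10 |
|---|---|---|---|
| Symptoms persisting on Day 14, woman stays in | Prohibited | Antibiotic provided | Counted as rescue (prolonged-treatment group only) |
| BV returns after Day 14, woman stays in | Prohibited | Not addressed | Not excluded, as no upper date limit is set |
| Woman withdraws | Not addressed | Antibiotic possible | No rule specific to withdrawal |

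The first row is a direct conflict. The second is a gap.

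**Step 2. How the SAP handles a woman whose BV returns between scheduled contacts**

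- *She withdraws before the last contact.* There is no scheduled *yes*, and 7.1.5 imputes nothing. Protocol 4.6 asks for end-of-study assessments at withdrawal where possible, but the SAP does not say whether that answer enters the Day 35/42 rate. Under 7.1.4 it may only be listed.
- *She is treated and stays in.* By the next call she may no longer need care and may answer *no*. Her antibiotic appears among the concomitant medications but not in the recurrence rate. If she was cured on Day 7, it enters no rescue endpoint either.
- *Denominator.* Under the 7.1.1 default she remains in it, so she counts in effect as not recurred. On an observed-data reading of 7.1.5 she is dropped if her answer is missing. Both lower the rate.

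**Step 3. Illustrative size**

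The documents give no expected recurrence rate for this product and no expected loss, so there is no planned figure to reproduce. Inputs:

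- 24 patients and a true cure rate of 70 % (protocol 9.3): 24 × 0.70 = 16.8, about 17 women cured on Day 7.
- Assumed recurrence of 9–30 % after 4 weeks (protocol Table 1, clindamycin cream, a different product): 17 × 0.09 = 1.5 and 17 × 0.30 = 5.1. I use 2 and 5 events.
- Number of recurrences lost: unknown, so varied.

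Rate with missing women kept in = (events − lost)/17. Rate on observed data = (events − lost)/(17 − lost). Intervals are two-sided 95 % Clopper-Pearson, as planned in SAP 7.9.2.

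| Events | Lost | Missing kept in | Observed only |
|---|---|---|---|
| 2 | 0 | 2/17 = 11.8 % (1.5–36.4) | same |
| 2 | 1 | 1/17 = 5.9 % (0.1–28.7) | 1/16 = 6.3 % (0.2–30.2) |
| 5 | 0 | 5/17 = 29.4 % (10.3–56.0) | same |
| 5 | 1 | 4/17 = 23.5 % (6.8–49.9) | 4/16 = 25.0 % (7.3–52.4) |
| 5 | 2 | 3/17 = 17.6 % (3.8–43.4) | 3/15 = 20.0 % (4.3–48.1) |
| 5 | 5 | 0/17 = 0 % (0–19.5) | 0/12 = 0 % (0–26.5) |

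With missing women kept in, each loss costs 1/17 = 5.9 points. On observed data the first loss costs 29.4 − 25.0 = 4.4 points with 5 events, or 11.8 − 6.3 = 5.5 points with 2.

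The Day 42 group is smaller: 24 × 0.30 = 7.2, about 7 women. With missing women kept in, one loss there costs at least 1/7 = 14.3 points.

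**The case against.** Several stronger readings are tempting, and the documents do not support them.

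- *A woman must withdraw to be treated.* No passage says so. 5.2.1 permits an antibiotic on withdrawal; it does not make withdrawal a condition of treatment. Withdrawal by the investigator is discretionary (4.4), non-compliance is only a listed possible reason (4.5), and 3.6 keeps women treated on Day 14 under safety follow-up.
- *The later gap contradicts the risk section.* 3.2.1 is about symptoms that persist to Day 14. On later recurrence it is silent. What does conflict with it is the unqualified ban in 5.7.
- *SAP 8.10 shows that rescue for later recurrence was intended.* It need not. The endpoint belongs to the prolonged-treatment group, whose Day 14 visit has a +2 day window, and rescue is a prescription. A later start date fits a prescription issued at that visit.
- *Recurrences are removed from the rate.* This is too strong. A *yes* on Day 14 or 21 counts at that visit, 4.6 seeks end-of-study assessments at withdrawal, 3.6 allows telephone collection from women who refuse visits, and 7.1.4 applies only in general.

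It is also fair to say that this is a secondary endpoint without a hypothesis test in a 24-patient feasibility study, and that the intervals above overlap widely.

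All of this stands, and it limits the point to a possible under-count of unknown size. It does not resolve the conflict between 5.7 and the Day 14 antibiotic, and it does not supply the missing SAP rule.

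**Conclusion.** The point holds in a limited form. Protocol 5.7 conflicts with 3.1, 3.2.1 and 5.2.1 over the Day 14 antibiotic. For BV returning after Day 14, the only antibiotic route stated is on withdrawal. Under SAP 8.8, 7.1.5, 7.1.4 and 7.1.1 together, a woman treated or withdrawn for returned BV without a scheduled *yes* counts in effect as not recurred, so the Day 35/42 rate can be biased low.

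The 5.9 points per loss at Day 35 rests on about 17 women cured and on missing women staying in the denominator. The total bias cannot be stated, because it depends on how many women are lost in this way. The primary Day 7 cure rate is not affected.

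**What to change.** 1. Reconcile protocol 3.2.1, 3.5.9, 5.2.1 and 5.7 and SAP 8.10 so that they give one consistent rule on antibiotic use during follow-up. Which clinical rule to adopt is for the sponsor and investigators; none is proposed here.
2. In SAP 8.8, state that the Day 35/42 rate counts as a recurrence (a) one reported at a withdrawal or unscheduled contact and (b) an antibiotic or withdrawal recorded as due to returned BV. State the denominator explicitly. In the same edit, extend 8.8 to women cured on Day 14: it now names only Day 7 cures, while the Day 21/42 endpoint is defined on Day 14 cures.
3. Make the remaining scheduled telephone contacts for any treated woman who has not withdrawn consent.

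Cost: amended protocol and SAP wording, with the ethics committee informed, and no new visits. The reason for each medication (5.7) and for withdrawal (4.6) is already to be recorded, though a woman may withdraw without giving a reason. The reported recurrence rate may come out somewhat higher.

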5.8 Treatment Compliance

Patients will be asked about investigational product administration by telephone on Day 4 and at the site on Day 7, and also on Day(s) 11 (telephone) and 14 (site) if receiving prolonged treatment. No other measurements of treatment compliance will be made.

6 CLINICAL PERFORMANCE

6.1 Clinical Performance Assessments

Assessments described below in [Section 6.1.1](#), gynecological examination, will be used to diagnose BV according to the following Amsel criteria:

1. Thin, white, yellow, homogenous discharge
2. Clue cells on microscopy (more than 20% of epithelial cells)
3. pH of vaginal fluid above 4.5
4. Release of fishy odor “i.e. a positive whiff test” when alkali (10% potassium hydroxide [KOH] solution) is added

Presence of 3 out of the 4 Amsel criteria above will serve as diagnosis of BV

Clinical cure is defined as absence of the following 3 Amsel criteria and is a primary study endpoint together with safety and tolerability evaluations:

1. Thin, white, yellow, homogenous discharge
2. Clue cells on microscopy (20% of epithelial cells)
3. Release of fishy odor “i.e. a positive whiff test” when alkali (10% potassium hydroxide [KOH] solution) is added

The Amsel score will also be used for the following secondary endpoints:

- Proportion of patients being negative for each of the 3 Amsel criteria on Day 7 compared to Day 0
- Recurrence rate on Day 14 and Day 35, defined as the proportion of patients clinically cured on Day 7 and thereafter responding “yes” to a yes/no question from the patient questionnaire on whether the symptoms have recurred
- Proportion of patients receiving prolonged treatment
- Clinical cure rate on Day 14, defined as the absence of all of the 3 Amsel criteria as defined above
- Proportion of patients being negative for each of the 3 Amsel criteria on Day 14 compared to Day 0
- Recurrence rate on Day 21 and Day 42, defined as the proportion of patients clinically cured on Day 14 and thereafter responding “yes” to a yes/no question from the patient questionnaire on whether the symptoms have recurred
- Proportion of patients receiving rescue treatment on Day 14

Assessments described in [Section 6.1.2](#), patient questionnaire, will be used to assess the following secondary endpoints:

- Proportion of patients having a reduction in the sum of the 3 BV symptoms scores (fishy smell, burning, irritation) on Day 4 and Day 7, compared to Day 0
- Proportion of patients having a reduction in the sum of the 3 BV symptoms scores (fishy smell, burning, irritation) on Day 11, Day 14, Day 21, and Day 42, compared to Day 0
- Change in the sum of the 3 BV symptoms scores (fishy smell, burning, and irritation) from Day 0 to Day 4 and Day 7
- Change in the sum of the 3 BV symptoms scores (fishy smell, burning, and irritation) from Day 0 to Day 11, Day 14, Day 21, and Day 42
- Usability, measured by patient questionnaire

6.1.1 Gynecological Examination

Patients will have gynecological examinations by the Investigator or an authorized designee on Day(s) 0 and 7; or Day(s) 0, 7, and 14 if receiving prolonged treatment, in order to assess presence of BV according to Amsel's criteria. At Day 0, a vaginal sample for bacterial culture will be taken to confirm diagnosis. Symptoms of BV (fishy smell, burning, and irritation) will also be assessed according to a scoring scale (0-3).

NOTE: Symptoms of BV (fishy smell, burning, and irritation) will always be assessed by patients themselves and asked about by the Investigator at site visits.

6.1.2 Patient Questionnaire

The questionnaire can be found in [Appendix 1](#).

The Clinical Trial Unit will call the patients on Day(s) 4, 14 and 35; or Day(s) 4, 11, 21, and 42 if receiving prolonged treatment; and ask questions from the patient questionnaire relating to BV symptoms, usability, concomitant medications, and AEs, if any.

Questions from *Section 1* in the patient questionnaire relating to BV symptoms will be asked to patients over telephone on Day(s) 4, 14, and 35; or Day(s) 4, 11, 21, and 42 if receiving prolonged treatment. A recurrence question will be asked to patients at Days(s) 14 and 35 if not receiving prolonged treatment and at Days(s) 21 and 42 if receiving prolonged treatment.

Questions from *Section 2* in the patient questionnaire relating to usability will be asked to patients on Day 7, and Day 14 if receiving prolonged treatment.

Questions from *Section 3* and *Section 4* in the patient questionnaire relating to concomitant medications and AEs, respectively, will be asked to patients at each visit/telephone contact.

7 SAFETY AND TOLERABILITY ASSESSMENTS

7.1 Medical and Surgical History

Medical and surgical history will be collected during the Screening Visit.

7.2 Clinical Laboratory Evaluation

Vaginal samples will be collected by vaginal swab on Day(s) 0 and 7 (and Day 14 if receiving prolonged treatment) by the Investigator and on Day 35 (or Day 42 if receiving prolonged treatment) by patients. Collected samples will be used accordingly:

- Samples collected on Day 0 will be sent to laboratory and cultured to confirm the BV diagnosis. Time for lab results is approximately 1 week.
- Samples collected on Day(s) 0, 7, 14, and 35 or 42 will be analyzed to assess the effects of the investigational product on the vaginal microbiome before treatment, after the treatment series, and at study end. Collected samples will be sent to laboratory sequencing present bacterial DNA content for complete species overview.

Patients' vaginal pH will be measured for assessments of investigational product *in vivo* duration on Day(s) 0 and 7. Vaginal pH lower at Day 7 compared to Day 0 indicate appropriate release duration.

